10.13. Appendix 13: Pharmacokinetic Sub-study Analysis Plan

10.13.1. Overview of Planned Pharmacokinetic Analyses

The pharmacokinetic (PK) analyses will be based on the “Pharmacokinetic” population, unless otherwise specified. The Pharmacokinetic population is defined as subjects for whom additional PK eligibility was confirmed and have at least one non-missing PK sample measurement.

Table 14 provides an overview of the planned analyses.

Table 14 Overview of Planned Pharmacokinetic Analyses for GSK1278863, and/or GSK2391220 (M2), GSK2506104 (M3) and GSK2531401 (M13)

Parameter	Untransformed						Log-Transformed							
	Stats Analysis			Summary		Individual		Stats Analysis			Summary		Individual	
	T	F	L	T	F	F	L	T	F	L	T	F	F	L
GSK1278863, GSK2391220 (M2), GSK2506104 (M3) and GSK2531401 (M13)														
GSK1278863 and Metabolites Plasma Pharmacokinetic Concentration Time Data (ng/ml) by Treatment				Y	Y ¹	Y	Y						Y ¹	Y
GSK1278863 and Metabolites Plasma Pharmacokinetic Parameter ² Data				Y			Y				Y			
GSK1278863														
GSK1278863 Dose Parameter Data				Y			Y							
GSK1278863 Special Parameter ³ Data				Y			Y				Y			

NOTES:

- T = Table, F = Figure, L = Listings, Y = Display generated.
- Stats Analysis = Represents TFL related to any formal statistical analyses (i.e. modelling) conducted.
- Summary = Represents TFL related to any summaries (i.e. descriptive statistics) of the observed raw data.
- Individual = Represents FL related to any displays of individual subject observed raw data.
 1. Mean and median plots will be generated
 2. Cmax, Tmax, Ctau
 3. Ctau/1mg Dose, Ctau/avg Dose EP TIR, Ctau/ avg Dose EP, Ctau/ Dose at MACE, Ctau/ Final Dose for subjects without MACE, Ctau/ Dose at MACE++, Ctau/ Final Dose for subjects without MACE++, Cmax/1mg Dose, Cmax/avg Dose EP TIR, Cmax/avg Dose EP, Cmax/ Dose at MACE, Cmax/ Final Dose for subjects without MACE, Cmax/ Dose at MACE++, Cmax/ Final Dose for subjects without MACE++

10.13.2. Drug Concentration Measures

Refer to [Appendix 5: Data Display Standards & Handling Conventions \(Section 10.5.3 Reporting Process & Standards\)](#).

10.13.3. Pharmacokinetic Parameters

10.13.3.1. Deriving Pharmacokinetic Parameters

- Refer to [Appendix 5](#): Data Display Standards & Handling Conventions (Section [10.5.3](#) Reporting Process & Standards).
- The pharmacokinetic parameters of parent GSK1278863, and metabolites (GSK2391220 (M2), GSK2506104 (M3), and GSK2531401 (M13)) will be calculated by programming methods.
- All calculations of non-compartmental parameters will be based on actual sampling times.
- Pharmacokinetic parameters described in [Table 15](#) will be determined from the plasma concentration-time data, as data permits.

Table 15 Derived Pharmacokinetic Parameters for GSK1278863, and/or GSK2391220, GSK2531403 and GSK2531401

Parameter	Parameter Description
GSK1278863, GSK2391220 (M2), GSK2506104 (M3) and GSK2531401 (M13)	
tmax	Time to reach Cmax, determined directly from the concentration-time data.
Ctau	Observed concentration at dosing interval (tau=24 h, predose sample)
Cmax	Maximum observed concentration, determined directly from the concentration-time data.
GSK1278863	
Avg Dose EP TIR	The average daily GSK1278863 dose when the subject is on-treatment and in target Hgb range during the evaluation period (EP) Weeks 28 – 52 (See Section 10.6.3.1). Evaluable Hgb values are used to determine time in range. Subjects who permanently stop randomized treatment before the beginning of the EP, and subjects who have 0% time in range (e.g., subjects who have an evaluable Hgb below or above range for the entire EP) will have a missing value for this parameter.
Avg Dose EP	The average daily GSK1278863 dose when the subject is on-treatment during the EP.
Dose at first MACE	The daily GSK1278863 dose at the time of the subject's first on-treatment adjudicated MACE. If the subject does not have an on-treatment adjudicated MACE, this value is missing.
Final Dose for Subjects without MACE	For subjects without an on-treatment adjudicated MACE, this is the subject's final GSK1278863 dose during the study.
Dose at first MACE++	The daily GSK1278863 dose at the time of the subject's first on-treatment adjudicated MACE++ (defined as the first adjudicated MACE, hospitalization for heart failure, or thromboembolic event) If the subject does not have an on-treatment adjudicated MACE++, this value is missing.
Final Dose for Subjects without MACE++	For subjects without an on-treatment adjudicated MACE++, this is the subject's final GSK1278863 dose during the study.
Ctau/1mg Dose	Ctau extrapolated to 1mg dose: Observed Ctau divided by dose administered on the PK day
Ctau/Avg Dose EP TIR	Ctau extrapolated to average dose during EP TIR: Ctau/1mg multiplied by the average daily GSK1278863 dose when the subject is on-treatment and in target Hgb range during Weeks 28-52 (see Section 10.6.3.1). Evaluable Hgb values are used to determine time in range.
Ctau/Avg Dose EP	Ctau extrapolated to average dose during EP: Ctau/1mg multiplied by the average daily GSK1278863 dose during the EP.
Ctau/Dose at first MACE	Ctau extrapolated to dose at first on-treatment adjudicated MACE: Ctau/1mg multiplied by the daily GSK1278863 dose at the time of the subject's first on-treatment adjudicated MACE.
Ctau/Final Dose for subjects without MACE	For subjects without an on-treatment adjudicated MACE, this is the subject's Ctau/1mg multiplied by the subject's final daily GSK1278863 dose during the study.

Parameter	Parameter Description
Ctau/Dose at first MACE++	Ctau extrapolated to dose at first on-treatment adjudicated MACE++: Ctau/1mg multiplied by the daily GSK1278863 dose at the time of the subject's first on-treatment adjudicated MACE++.
Ctau/Final Dose for subjects without MACE++	For subjects without an on-treatment adjudicated MACE++, this is the subject's Ctau/1mg multiplied by the subject's final daily GSK1278863 dose during the study.
Cmax/1mg Dose	Cmax extrapolated to 1mg dose: Observed Cmax divided by dose administered on the PK day
Cmax/Avg Dose EP TIR	Cmax extrapolated to average dose during EP TIR: Cmax/1mg multiplied by the average daily GSK1278863 dose when the subject is on-treatment and in target Hgb range during Weeks 28-52 (see Section 10.6.3.1). Evaluable Hgb values are used to determine time in range.
Cmax/Avg Dose EP	Cmax extrapolated to average dose during EP: Cmax/1mg multiplied by the average daily GSK1278863 dose during the EP.
Cmax/Dose at first MACE	Cmax extrapolated to dose at MACE: Cmax/1mg multiplied by the daily GSK1278863 dose at the time of the subject's first on-treatment adjudicated MACE.
Cmax/Final Dose for subjects without MACE	For subjects without an on-treatment adjudicated MACE, this is the subject's Cmax/1mg multiplied by the subject's final daily GSK1278863 dose during the study.
Cmax/Dose at first MACE++	Cmax extrapolated to dose at MACE++: Cmax/1mg multiplied by the daily GSK1278863 dose at the time of the subject's first on-treatment adjudicated MACE++.
Cmax/Final Dose for subjects without MACE++	For subjects without an on-treatment adjudicated MACE++, this is the subject's Cmax/1mg multiplied by the subject's final daily GSK1278863 dose during the study.

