Study Design	
 This is a randomized, open-label (sponsor blind), active-controlled, parallel-group, multi-center, event-driven study in non-dialysis subjects with anemia associated with chronic kidney disease (CKD). This study will comprise 4 study periods: a 4-week screening period, a 4-week placebo run-in period, a treatment period, and a follow-up period. Prior erythropoiesis-stimulating agent (ESA) therapy, if present, continues during the screening and run-in periods. ESAs refer to any rhEPO or methoxy PEG-epoetin beta. The total duration of the study is dependent upon the accumulation of at least 664 adjudicated first MACE (i.e., it is event-driven) unless review of interim data by the Independent Data Monitoring Committee (IDMC) recommends bringing the study to an earlier close. Subjects will be stratified by region, by whether they are currently using an ESA and by participation in the ambulatory blood pressure monitoring (ABPM) sub-study. Region and ESA use at study entry are considered to be stratification factors that are potentially prognostically important, i.e., predictive of study endpoints while participation in the ABPM sub-study is an administrative stratification factor intended solely to ensure a similar number of sub-study subjects in each of the two randomized groups. Following stratification, subjects will be randomized 1:1 to receive oral daprodustat or subcutaneous (SC) darbepoetin alfa.

Overview	Key Elements of the RAP
	
 Both treatment arms (daprodustat and darbepoetin alfa) will follow a protocol-specified randomized treatment dose adjustment algorithm to achieve and/or maintain Hgb within the target range of 10-11 g/dL inclusive. Dose changes will be made programmatically by the Interactive Response Technology (IRT) system for both randomized treatment arms.

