PK sub-study endpoints include: 
 Scatter plots of daprodustat PK parameters (C_{tau} and C_{max}) dose normalized to 1 mg vs. percent time in range during EP. Scatter plots of average daprodustat dose during EP vs. percent time in range during EP. Scatter plots of daprodustat PK parameters (C_{tau} and C_{max}) dose normalized to average dose during EP vs. percent time in 	PK sub-study endpoints modified as follows: 
 Endpoints removed: Scatter plots of daprodustat PK parameters (C_{tau} and C_{max}) dose normalized to 1 mg vs. percent time in range during EP. Scatter plots of average daprodustat dose during EP while in target Hgb range vs. percent time in range 	
 Removed as these endpoints do not provide additional information for efficacy explorations than what will be available from remaining endpoints.

Protocol	Reporting & Analysis Plan	
Statistical Analysis Plan	Statistical Analysis Plan	Rationale for Changes

range during EP.
 
 Scatter plots of daprodustat PK parameters (C_{tau} and C_{max}) dose normalized to 1 mg vs. change from baseline of Hgb during EP. Boxplots of daprodustat PK parameters (C_{tau} and C_{max}) dose normalized to 1 mg by subjects with or without MACE or combined safety endpoint 	
during EP.
 
 Scatter plots of daprodustat PK parameters (C_{tau} and C_{max}) dose normalized to average dose during EP while in target Hgb range vs. percent time in range during EP. Endpoints removed: Scatter plots of daprodustat PK parameters (C_{tau} and C_{max}) dose normalized to 1 mg vs. change from baseline of Hgb during EP. Endpoints removed: Boxplots of daprodustat PK parameters (C_{tau} and C_{max}) dose normalized to 1 mg by subjects with or without MACE or combined safety endpoint 	
ABPM Sub-study Statistical Analysis Plan	ABPM Sub-study Statistical Analysis Plan	Rationale for Changes

 Statistical analyses planned. 	
 No statistical analysis will be conducted for this sub-study due to the small number of subjects recruited. Instead all data will either be summarized or listed. 	
 Small number of subjects recruited.

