 - Rows outlining scenarios involving combinations of scheduled and unscheduled Hgb values of the same type apply to all Hgb summaries and analysis.

Scheduled Central Lab Hgb Value	Unscheduled Central Lab Hgb Value	Scheduled HemoCue Hgb Value	Unscheduled HemoCue Hgb Value	Value to Use	Type/Label
x				Scheduled central lab Hgb value	Scheduled visit
	x			Unscheduled central lab Hgb value	Unscheduled
		x		Scheduled HemoCue Hgb value	Scheduled visit
		multiple ¹		Average of scheduled HemoCue Hgb values	Scheduled visit
			x	Unscheduled HemoCue Hgb value	Unscheduled
	multiple			Average of unscheduled central lab Hgb values	Unscheduled
			multiple	Average of unscheduled HemoCue Hgb values	Unscheduled
x	x			Average of central lab Hgb values	Scheduled visit
x		x		Scheduled central lab Hgb value	Scheduled visit
x			x	Scheduled central lab Hgb value	Scheduled visit
	x	x		Unscheduled central lab Hgb value	Unscheduled
	x		x	Unscheduled central lab Hgb value	Unscheduled
		x	x	Average of HemoCue Hgb values	Scheduled visit

1: The dose adjustment algorithm will require sites to obtain two HemoCue Hgb values at some visits.

Time In Range

Time in Range During the EP

- Number of days that a subject's evaluable Hgb is within the analysis range of 10-11.5 g/dL inclusive during the EP (See Section 10.6.1), including any unscheduled evaluable Hgb values that were taken during this time period.
- Use of unscheduled Hgb values follows the scenarios for unscheduled and multiple Hgb values.
- Linear interpolation is used to estimate Hgb between visits, accounting for any intermittent missing values [Rosendaal, 1993].

Percent Time in Range During the EP

- Time in Range During the EP / [Earlier of (Date of the last evaluable Hgb value, Week 52 visit date) – Later of (Date of the first evaluable Hgb value that between Week 16 and Week 52

Time In Range

inclusive, Week 28 visit date)]
 
 Note: Percent time in/below/above range during the EP is only defined for subjects with a Treatment Stop Date that is on or after their Week 28 visit date, and have at least two evaluable Hgb values on different days, where at least one evaluable Hgb value is contained within the EP and another evaluable Hgb value occurs within the range of the Week 16 visit through 4 weeks following the Week 52 visit, inclusive.
Time in Range During the MP

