10.13.4. Pharmacokinetic / Pharmacodynamic Analyses

- The primary goal of this analysis is to characterize the pharmacokinetic/pharmacodynamic relationship of parent GSK1278863 and efficacy and safety endpoints in the “Pharmacokinetic” population from this study.
 - The influence of subject demographics and baseline characteristics, including disease activity in this population may be investigated.
- A summary of the planned population pharmacokinetic/pharmacodynamic analyses are outlined below:
 - Relationships between drug exposure and selected efficacy, MACE and MACE ++ events will be explored and characterized as data permit. The exposure will be estimated on the sparse PK collected in a sub-set of the study population. The data may be dose- extrapolated to the dose administered during the PK collection period. Any changes to the proposed analyses would be described in the CSR.

Table 16 Overview of Planned Pharmacokinetic Pharmacodynamic Analyses for GSK1278863

Parameter	Untransformed						Log-Transformed							
	Stats Analysis			Summary		Individual		Stats Analysis			Summary		Individual	
	T	F	L	T	F	F	L	T	F	L	T	F	F	L
GSK1278863														
Scatter plot of % Time Evaluable Hgb in Range during EP vs. Avg Dose EP TIR						Y								
Scatter plot of Evaluable Hgb Change from Baseline during EP vs. Avg Dose EP						Y								
Scatter plot of % Time Evaluable Hgb in Range during EP vs. Ctau/Avg Dose EP TIR						Y								
Scatter plot of Evaluable Hgb Change from Baseline during EP vs. Ctau/Avg Dose EP						Y								
Boxplot of Ctau/Dose at on-treatment MACE or MACE++ by subjects with or without on-treatment MACE or MACE++						Y								
Scatter plot of % Time Evaluable Hgb in Range during EP vs. Cmax/Avg Dose EP TIR						Y								
Scatter plot of Evaluable Hgb Change from Baseline during EP vs. Cmax/Avg Dose EP						Y								
Boxplot of Cmax/Dose at on-treatment MACE or MACE++ by subjects with or without on-treatment MACE or MACE++						Y								

NOTES :

- T = Table, F = Figure, L = Listings, Y = Display generated.
- Stats Analysis = Represents TFL related to any formal statistical analyses (i.e. modelling) conducted.
- Summary = Represents TFL related to any summaries (i.e. descriptive statistics) of the observed raw data.
- Individual = Represents FL related to any displays of individual subject observed raw data.

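### All three time-in-range PK plots average dose over in-range days only, so subjects with 0% time in range cannot be plotted

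*SAP*

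**What the plan says.** SAP Section 10.13.4, Table 16, lists three plots with percent time in range as the response:

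- "Scatter plot of % Time Evaluable Hgb in Range during EP vs. Avg Dose EP TIR"
- "Scatter plot of % Time Evaluable Hgb in Range during EP vs. Ctau/Avg Dose EP TIR"
- "Scatter plot of % Time Evaluable Hgb in Range during EP vs. Cmax/Avg Dose EP TIR"

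SAP Section 10.13.3.1, Table 15, defines Avg Dose EP TIR as the daily dose averaged while the subject is on treatment and in the target Hgb range during Weeks 28 to 52. For 0% time in range it says that "subjects who have an evaluable Hgb below or above range for the entire EP) will have a missing value for this parameter". The Ctau and Cmax versions are the 1 mg value multiplied by that same in-range dose.

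Section 10.6.3.1 defines the response from the days on which evaluable Hgb is "within the analysis range of 10-11.5 g/dL inclusive during the EP".

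As background, Section 2.1 records that the protocol's dose plot was "Scatter plots of average daprodustat dose during EP vs. percent time in range during EP", that is, with the dose averaged over the whole EP. It also records that plots against PK parameters normalized to 1 mg were removed. That history is not itself an error.

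**The concern.** The exposure on the horizontal axis is computed only from days on which the response on the vertical axis was good. At the worst value of the response there are no such days, so the point is undefined and drops out. The plots are thus selected on the outcome they display. For subjects near the bottom of the scale, the plotted exposure is the dose during a brief in-range spell, and the dosing during the rest of the EP is ignored.

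Section 10.13.4 gives the aim as characterizing how exposure to the drug relates to efficacy and safety endpoints. For time in range, the planned plots cannot show what exposure accompanied complete failure to be in range. A reader who sees no pattern in them could not tell an absent relation from one whose lower end was cut off by definition.

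**Working it through.** No sample size, power or alpha figure is involved, and the SAP states no figure to reproduce. The check traces each time-in-range plot to its variables.

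**Step 1. Response for a subject never in range.** Section 10.6.3.1 gives percent time in range as in-range days divided by the observed EP days between evaluable Hgb values. It is defined if treatment stopped on or after the Week 28 visit and there are at least two suitably placed evaluable Hgb values. Take a subject on treatment throughout, with every value below 10 g/dL (or every value above 11.5 g/dL). With a full EP of 52 - 28 = 24 weeks = 168 days, the response is 0 / 168 = 0%. It exists.

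**Step 2. Exposure for the same subject.** Avg Dose EP TIR is the sum of daily doses over in-range days divided by the number of in-range days. That number is 0, so Table 15 sets the value to missing. Ctau/Avg Dose EP TIR = (Ctau/1 mg) x Avg Dose EP TIR, so it is missing too, and likewise for Cmax.

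**Step 3. Count the plots.**

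| Response | Exposure variable | Loses 0% subjects by rule? |
|---|---|---|
| % time in range | Avg Dose EP TIR | yes |
| % time in range | Ctau/Avg Dose EP TIR | yes |
| % time in range | Cmax/Avg Dose EP TIR | yes |
| Hgb change | Avg Dose EP | no |
| Hgb change | Ctau/Avg Dose EP | no |
| Hgb change | Cmax/Avg Dose EP | no |

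The MACE and MACE++ boxplots use the dose at the event or the final dose, so the rule does not touch them. All 3 of 3 time-in-range plots are affected and none of the others.

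**Step 4. Subjects just above 0%.** At 5% time in range over 168 days, the exposure rests on 0.05 x 168 = 8.4 days. The remaining 159.6 days do not enter.

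**Step 5. Early stoppers.** Table 15 also sets the value to missing for subjects who stop treatment before the EP. This is no further loss, because Section 10.6.3.1 already leaves their percent time in range undefined.

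**Step 6. Range wording.** Table 15 speaks of the target Hgb range. In the Synopsis the dosing aim is to "maintain Hgb within the target range of 10-11 g/dL inclusive". Table 15, however, points to Section 10.6.3.1, whose only range is 10-11.5 g/dL. If 10-11 were programmed by mistake, a subject steady at 11.2 g/dL would have a response of 100% and a missing exposure.

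**Step 7. After the fix.** Avg Dose EP averages over all on-treatment EP days, so it does not depend on the subject having been in range. With it and its Ctau and Cmax versions on the axis, the plots losing 0% subjects by this rule fall from 3 of 3 to 0 of 3.

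**The case against.** Four points deserve weight.

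- **Scope.** A reader might infer that the worst responders vanish from the exposure-response work altogether. They do not. The three Hgb-change plots already use Avg Dose EP and keep these subjects, and the Avg Dose EP versions of Ctau and Cmax are among the parameters summarized and listed under Table 14. This stands and limits the point to three figures.
- **Titration.** Both arms are dosed by an algorithm steering Hgb to its target, so dose follows Hgb. Avg Dose EP is response-driven as well, and a plot against it shows no causal relation. One could also argue that the dose while in range answers a different question, namely at what exposure a subject is in range, though the SAP does not give that reason. The confounding stands for either axis. It does not justify a rule that makes the lowest response value unplottable.
- **Disclosure.** The missing-value rule is written in Table 15 and the change is listed in Section 2.1, so nothing is hidden. But the rationale recorded there covers the removed plots only, on the ground that the remaining ones suffice, and every remaining time-in-range plot drops the 0% subjects.
- **Range label.** A reader might see a contradiction between 10-11 and 10-11.5 g/dL. The cross-reference to Section 10.6.3.1 largely settles it as 10-11.5, so this is loose wording.

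**Conclusion.** The point holds for the three time-in-range plots in Table 16. Subjects wholly below or wholly above range have a response of 0% and are left out by definition, and subjects with little time in range are placed at the dose of a few days.

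It is minor. Table 16 marks these as individual figures in an exploratory sub-study, with no model, test or decision attached, and no co-primary, principal secondary or main safety conclusion rests on them.

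It is tempting to say by how much the omission weakens the apparent relation. The document does not support any figure. The share of subjects at 0% is not given. Time in range is not monotone in exposure, since too little and too much both lead to 0%. Under titration even the direction of the association between dose and time in range is open. A simulated loss of correlation would only reflect the mean Hgb, spread and dosing model put into it. The exclusion itself follows from the definitions and needs none of those assumptions.

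**What to change.** In Table 16, add plots of percent time in range against Avg Dose EP, Ctau/Avg Dose EP and Cmax/Avg Dose EP, or substitute them for the current three. If the EP TIR versions are kept, label them secondary and footnote on each the number of subjects omitted for 0% time in range. In Table 15, replace the reference to the target Hgb range with the 10-11.5 g/dL analysis range of Section 10.6.3.1, in the dose, Ctau and Cmax definitions alike.

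The cost is SAP wording and at most three extra exploratory figures (none if substituted). No new data or derivations are needed. A line stating that the plots remain descriptive because dose is titrated to Hgb would guard against over-reading either version.

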10.2. Appendix 2: Time & Events

10.2.1. Protocol Defined Time & Events

10.2.1.1. Schedule of Assessments Year 1 to the End of the Study

Protocol activity (visits ±1 week, except Weeks 2 and 4 which are ±3 days) (Note: All visit timings are relative to Day 1)	Screen Week -8	Run-in Week -4	Day 1 through Week 52					
			Day 1 ¹³	Week 2	Full study visit Week 4, 16, 28, 40	Abbreviated study visit Week 8, 12, 20, 24, 32, 36, 44, 48	Week 52	Unscheduled ¹⁰
Informed Consent (main study)	X ²⁰							
IRT system transaction	X	X	X	X	X	X	X	X
Subject reminder, inform site staff of changes in health ¹			X				X	
Check/confirm entry criteria, weight	X		X					
History: medical, hospitalization, transfusion demography, height	X							
SBP/DBP, HR (single readings unless otherwise indicated)	X	X	X (triplicate)	X	X	X	X (triplicate)	X
ECG			X ¹⁷				X	
Ultrasound of kidneys and adrenal glands		X ¹⁶						
Placebo run-in or randomized treatment dispensing (start administration on day of dispensing)		X (placebo)	X	X ⁹	X	X	X	X ⁹
Placebo run-in or randomized treatment compliance			X (placebo)	X ¹¹	X	X	X	X ¹¹
Iron therapy, transfusions ²	X	X	X	X	X	X	X	X
Rescue medication(s) for Initial Intervention ^{2,3}					X	X	X	
Females only: estradiol and FSH (if required)	X							
FRP only: urine pregnancy test ^{4,18}		X	X		X		X	
HemoCue Hgb	X	X	X	X	X	X	X	X
Hematology ⁵	X	X	X		X	Hgb only	X	X
Clinical chemistry ⁵	X		X		X		X	X
Ferritin, total iron, UIBC ⁵	X		X		X		X	
Hepcidin			X		X		X	
HbA1c ⁶ , lipids (non-fasting)			X				X	
hsCRP, iPTH			X		Wk 28		X	
Urine albumin/ creatinine ratio			X		Wk 4, Wk 28		X	

CONFIDENTIAL

200808

Protocol activity (visits ±1 week, except Weeks 2 and 4 which are ±3 days) (Note: All visit timings are relative to Day 1)	Screen Week -8	Run-in Week -4	Day 1 through Week 52					
			Day 1 ¹³	Week 2	Full study visit Week 4, 16, 28, 40	Abbreviated study visit Week 8, 12, 20, 24, 32, 36, 44, 48	Week 52	Unscheduled ¹⁰
Storage biomarkers (blood, urine) ¹⁹			X		Wk 28		X	
Hospitalization ² , transition to dialysis ^{2,7} , kidney transplant ²				X	X	X	X	X
Non-serious AEs, SAEs, AEs of special interest, clinical events	X ⁸	X	X	X	X	X	X	X
Review concomitant medications	X	X	X	X	X	X	X	X

Schedule of Assessments Year 1 to End of Study (Continued)

Protocol activity (visits ±1 week) (Note: All visit timings are relative to Day 1)	Year 2				Year 3				Year 4					Unscheduled ^{10,12}	End of Study ¹⁵	Follow-up (4-6 weeks after stopping randomized treatment)	

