6. Baseline ABPM and 24 hour urine will be performed at Week -4 or at an unscheduled visit up until 1 week prior to randomization (Day 1).
7. Subject will record sleep and awake times during the ABPM session
8. Informed consent for PK sub-study can be obtained anytime from Day 1 (once the subjects is confirmed to have been randomized to daprodustat) till Week 52, i.e., last study visit where PK sampling can be obtained.
9. Blood samples will be collected at any single study visit from the Week 4 through Week 52 visit (i.e., PK is collected at one visit only, based on convenience for the subject/site).
10. For subjects transitioning to dialysis, 24 hour urine collection to be done as able.

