10.6.3.6. Dose Adjustment Scheme Endpoints

Dose Adjustment Scheme Endpoints																				
General																				

 • The IRT system assigns all randomized treatment doses in accordance with the dose adjustment scheme specified in the protocol. • During the study, it is possible for subjects to change randomized treatment doses at both scheduled and unscheduled visits. • Sites are instructed to complete an exposure record every time dosing instruction is received from the IRT, with the exception of re-dispensing situations where the subject is instructed to continue using the same randomized treatment. 																				
Daprodustat Doses																				

Sites will enter the dose of daprodustat into exposure records – the daily frequency will be auto-populated for this randomized treatment. The dose steps of daprodustat are shown below:
 
  
 Total Daily Dose	How Administered	
   
 1 mg	single 1 mg tablet	
 
 2 mg	single 2 mg tablet	
 
 4 mg	single 4 mg tablet	
 
 6 mg	single 6 mg tablet	
 
 8 mg	single 8 mg tablet	
 
 10 mg	single 10 mg tablet	
 
 12 mg	two 6 mg tablets	
 
 16 mg	two 8 mg tablets	
 
 24 mg	three 8 mg tablets	
  
	Total Daily Dose	How Administered	1 mg	single 1 mg tablet	2 mg	single 2 mg tablet	4 mg	single 4 mg tablet	6 mg	single 6 mg tablet	8 mg	single 8 mg tablet	10 mg	single 10 mg tablet	12 mg	two 6 mg tablets	16 mg	two 8 mg tablets	24 mg	three 8 mg tablets
Total Daily Dose	How Administered																			
1 mg	single 1 mg tablet																			
2 mg	single 2 mg tablet																			
4 mg	single 4 mg tablet																			
6 mg	single 6 mg tablet																			
8 mg	single 8 mg tablet																			
10 mg	single 10 mg tablet																			
12 mg	two 6 mg tablets																			
16 mg	two 8 mg tablets																			
24 mg	three 8 mg tablets																			
Darbepoetin Alfa Doses																				

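### Ctau is a predose trough but is divided by the PK-day dose, so Ctau/1mg and everything built on it is wrong when a new dose starts at the PK visit

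*SAP*

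**What the plan says.** Table 15 (SAP Section 10.13.3.1) describes Ctau as "Observed concentration at dosing interval (tau=24 h, predose sample", that is, a trough drawn before the day's dose. It then derives the 1 mg value as "Ctau extrapolated to 1mg dose: Observed Ctau divided by dose administered on the PK day". The peak is treated in the same way: "Cmax extrapolated to 1mg dose: Observed Cmax divided by dose administered on the PK day".

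The other Ctau parameters in Table 15 are Ctau/1mg multiplied by a later or average dose: the average over the EP, the average while in Hgb range during the EP, the dose at first MACE or MACE++, or the final dose for subjects without such an event.

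On timing, the schedule in Section 10.2.1.2 states "Blood samples will be collected at any single study visit from the Week 4 through Week 52 visit". Section 10.2.1.1 lists "Placebo run-in or randomized treatment dispensing (start administration on day of dispensing". Section 10.6.3.6 notes that "it is possible for subjects to change randomized treatment doses at both scheduled and unscheduled visits". Changes are made under a "dose adjustment algorithm to achieve and/or maintain Hgb within the target range of 10-11 g/dL inclusive" (Section 1). Section 10.6.1 adds that the algorithm includes a zero dose, or hold.

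The PK appendix has no rule that uses the prior dose, sets aside PK days with a dose change, or deals with a zero dose.

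**The concern.** A sample drawn before a dose cannot contain drug from that dose. The PK-day dose is the natural divisor for a post-dose peak, but for a trough it is right only if it equals the dose taken before. PK visits are ordinary visits at which the dose can change, so the two need not be equal.

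Where they differ, Ctau/1mg is no longer concentration per mg of the dose that produced it. The error is systematic: it understates exposure after an increase and overstates it after a decrease. Since the algorithm steers Hgb, the sign of the error at the visit is related to Hgb at that visit. At stake are the Ctau/1mg summaries and listing in Table 14, the other extrapolated Ctau parameters, and the three Ctau displays in Table 16: time in range against Ctau at the in-range EP dose, Hgb change against Ctau at the average EP dose, and the MACE/MACE++ boxplot.

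**Working it through.** The SAP gives no figure on this point, so there is none to reproduce. The check is arithmetic on its own dose steps.

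**Inputs.** Daprodustat steps in Section 10.6.3.6: 1, 2, 4, 6, 8, 10, 12, 16 and 24 mg daily. Zero dose: Section 10.6.1. Definitions of Ctau and Ctau/1mg: Table 15.

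**Assumptions.** The trough is proportional to dose and reflects only the previous dose. The new dose is first taken on the PK day. The number of steps in one change is not in the SAP, which refers to the protocol for the adjustment scheme (Section 2.3), so one step is taken as the base case and two steps as a range.

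**Formula.** Let c be the correct trough per mg, P the previous dose and D the PK-day dose. Observed Ctau = c × P. As written, Ctau/1mg = c × P / D. The ratio to the correct value is P / D.

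**One-step changes**

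| Steps (mg) | Increase, P/D | Decrease, P/D |
|---|---|---|
| 1 and 2 | 1/2 = 0.50 | 2.00 |
| 2 and 4 | 2/4 = 0.50 | 2.00 |
| 4 and 6 | 4/6 = 0.67 | 1.50 |
| 6 and 8 | 6/8 = 0.75 | 1.33 |
| 8 and 10 | 8/10 = 0.80 | 1.25 |
| 10 and 12 | 10/12 = 0.83 | 1.20 |
| 12 and 16 | 12/16 = 0.75 | 1.33 |
| 16 and 24 | 16/24 = 0.67 | 1.50 |

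The error is two-fold only between 1 and 2 mg and between 2 and 4 mg. Elsewhere it is 1.2- to 1.5-fold.

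**Two-step changes.** The extreme is between 1 and 4 mg: 1/4 = 0.25 upward and 4/1 = 4.00 downward. Other pairs run from 0.33 (2 to 6 mg) to 0.67 (8 to 12 mg) upward, with the reciprocals downward.

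**Holds.** If a hold ends on the PK day, P = 0: the trough is near zero and is divided by a full dose. If the PK-day dose is zero, D = 0 and the ratio is undefined.

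**Carry-through.** Multiplying by another dose leaves P / D unchanged. Take a subject who goes from 4 to 6 mg on the PK day and has an average EP dose of 6 mg. The correct Ctau at the average EP dose is 6c. As written it is (4c/6) × 6 = 4c, again 0.67 of the correct value.

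**After correction.** With divisor P the ratio is P / P = 1.00 for every non-zero previous dose.

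**The case against.** The strongest reply is that the SAP does not say which dose is taken on the PK day. The sampling procedure belongs to the protocol's PK appendix, which is not at hand. If subjects always took the old dose that day, or if the dose did not change, there would be no error. This stands as a limit on how often the problem occurs. It does not rescue the definition: the schedule points to a new dose starting on the day it is dispensed, Table 15 has no safeguard, and the prior-dose divisor is right in either case.

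The second reply concerns consequence. The PK analysis uses a subset with sparse sampling, it is exploratory, Table 16 marks only individual figures with no statistical analysis, and Section 10.13.4 leaves changes to be described in the CSR. This stands in full and sets the severity.

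A reader might go further and infer that the planned plots will show a spurious positive relation between exposure and Hgb of some predictable size. The SAP does not support that. Section 2.1 records that the plots of 1 mg-normalized parameters were removed, and what remains plots Ctau/1mg multiplied by a dose. Only one Ctau display, Hgb change against Ctau at the average EP dose, has an axis on which a signed Hgb bias would show directly. Time in range falls for both low and high Hgb, so opposite errors tend to cancel, and the boxplot is by MACE or MACE++. The Hgb levels that trigger a dose change and the share of PK visits with a change are not in the SAP, so any correlation would rest on assumed inputs.

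**Conclusion.** Wrong as written, low severity. The Ctau/1mg rule in Table 15 pairs a trough with a dose that had not been taken when the sample was drawn. If a new dose is first taken at the PK visit, a one-step change puts Ctau/1mg at 0.50 to 0.83 of the correct value after an increase and at 1.2 to 2.0 times it after a decrease, and all extrapolated Ctau parameters carry the same factor. Two-fold should not be read as an upper bound, because multi-step changes and holds can exceed it or leave the ratio undefined.

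These sizes assume a dose-proportional trough that reflects the previous dose alone. How many subjects are affected cannot be derived from the SAP. No size of correlation in the planned plots is claimed. Cmax/1mg is correctly defined. No co-primary or principal secondary analysis uses Ctau.

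**What to change.** In Table 15, define Ctau/1mg as observed Ctau divided by the last dose actually taken before the predose sample, read from the exposure record in force on the preceding day. Set it to missing when the preceding period was a hold or zero dose. Keep the PK-day dose as divisor for Cmax/1mg only. Carry the corrected Ctau/1mg into all Ctau-derived parameters in Tables 14 to 16.

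The cost is one changed definition and a small programming change. The exposure records already hold the prior dose, and Section 10.6.3.6 already derives a most recent dose before a scheduled visit. The downside is that a few Ctau values become missing after dose holds. Nothing in dosing or sampling changes.
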